6.1. Population Pharmacokinetic Analysis

6.1.1. Pharmacokinetic Modeling: The PK data will be analyzed using a population PK modeling approach through the nonparametric adaptive grid (NPAG) algorithm in the Pmetrics™ package for the R environment.^{21,22} Models will be parameterized as one- and two-compartment systems with zero-order infusion and elimination from the central compartment modeled as a first-order process. Michaelis-Menten and mixed-order linear/Michaelis-Menten elimination will be tested if first-order processes alone do not display adequate fit of the data.

For all models, the inverse of the estimated assay variance will be used as the first estimate for weighting. Weighting will be accomplished by making the assumption that total observation variance is proportional to assay variance. Assay variance will be determined on a between-day basis. The analysis will be performed with adaptive γ , a scalar which is optimized with each cycle to produce the best approximation to the homoscedastic assumption.

Models will be run for at least 100 cycles and Bayesian estimates will be obtained for each patient. For each model, both the mean and median will be employed as measures of central tendency for the population parameter estimates and will be evaluated in the Bayesian analysis. Scatter plots will be examined for individual patients and for the population as a whole.

6.1.2. Monte Carlo Simulation: The parameter vector and covariance matrix from population PK modeling will be used as the prior distribution for the simulation function within Pmetrics™. 1000-subject Monte Carlo simulations will be performed for candidate dosing regimens.

The simulated plasma concentration-time curves will be used to calculate area under the concentration-time curve (AUC) values for different 24-hour increments through 96 hours. For each regimen examined, probability of efficacy will be the fraction of the simulated subjects at each time interval for which the 24-hour AUC is between 50 – 100 mg*h/L while the probability of toxicity will be the fraction of subjects with 24-hour AUC values ≥ 100 mg*h/L.^{23,24}

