We propose to measure the plasma concentrations of PMB in adult patients with CF receiving intravenous therapy as a part of their routine care and to use these measured concentrations to build population pharmacokinetic models. The population pharmacokinetic modeling approach will allow the assessment of the impact of patient specific covariates (i.e. weight, renal function) on pharmacokinetic parameters. Patients will be monitored for nephrotoxicity and neurotoxicity to ensure that PMB has an acceptable

margin of safety in this patient population. This investigation will be the first to prospectively assess the pharmacokinetics and toxicities of PMB in this patient population and will facilitate optimal use of this compound in the management of acute pulmonary exacerbations of CF.

4. Specific Aim/Hypothesis

4.1. Measure the plasma concentration of PMB in adult CF patients receiving intravenous therapy. Adult patients with CF often receive multiple courses of antipseudomonal antibiotics over the course of their disease resulting in the evolution of multi-drug resistant (MDR) *P. aeruginosa* pulmonary colonizers. The polymyxins, colistin and PMB, frequently retain activity against MDR gram-negative bacteria. Colistin has historically been the most commonly used polymyxin in patients with CF; however, new pharmacokinetic (PK) and toxicity data obtained from non-CF populations suggest that PMB may achieve more consistent exposure with lower associated toxicity. We aim to measure concentrations of PMB in plasma samples obtained from adult CF patients treated with polymyxin B using liquid chromatography–tandem mass spectrometry (LC-MS/MS).

4.2. Characterize the pharmacokinetics of PMB in adult CF patients. There are three major population PK studies which inform the dosing of PMB and one small study including patients with CF. These studies suggest that the clearance of PMB is not related to patient body weight and have discordant results regarding patient renal function. Therefore, underweight patient populations with excellent renal function, such as CF, may be at risk for underdosing with traditional weight-based regimens. We aim to use population pharmacokinetic modeling to characterize the PK of fixed-dose PMB in this special population and assess the effect of patient-specific covariates (e.g., body weight, renal function) on PK parameters.

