5.6. Dosing and Administration

5.6.1. The dose and duration of infusion for PMB will be determined at the discretion of the prescribing physician in the course of routine clinical care. There is no study intervention on the dosing and administration of PMB.

5.6.2. The recommended dosing schedule for intravenous polymyxin B at Michigan Medicine consists of an initial weight-based loading dose (2 mg/kg, maximum of 200 mg) followed by 100 mg every 12 hours for the duration of therapy as determined by the clinician. A reduction of the maintenance dose to 75 mg every 12 hours is recommended for patients with total body weight less than or equal to 50 kg.

5.7. Sampling:

5.7.1. Blood samples will be collected from enrolled patients at 5 time points during a single dosing interval under steady-state conditions. Sampling will occur on any day of therapy immediately prior to and following a single dose of PMB. The infusion time is selected at the discretion of the prescribing physician; thus the sampling schema is described based on the duration of infusion (Table 1).

Table 1: Sample collection times

Sample Code	Collection Timepoint	Collection Time Relative to Duration of Infusion (t_{inf})
C_0	Prior to Start of Infusion	0 hour
C_1	End of Infusion	$t_{inf} + 0$ hour
C_2	One Hour after End of Infusion	$t_{inf} + 1$ hour
C_3	Three Hours after End of Infusion	$t_{inf} + 3$ hours
C_4	Eight Hours	8 hours

5.7.2. Blood samples will be collected via one of three sampling methodologies: peripheral venipuncture, peripheral intravenous catheter, or a central venous catheter (e.g., PICC, Port). The method of obtaining blood samples will be determined by study personnel and will consider patient preference, patient safety, and the likelihood of obtaining adequate samples. Insertion of, care for, and sampling from indwelling catheters will be performed per hospital policy.

5.7.3. The procedure for obtaining and processing blood samples can be found in the Laboratory Protocol document in the Appendix (10.1).

5.8. Demographic and Clinical data: Study team members will obtain demographic and clinic data needed to describe the study population and build pharmacokinetic models. Data will be abstracted from DataDirect or obtained directly from the medical record for each index encounter. Data recorded directly from the medical record will be stored in REDcap.

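### Does Section 6.1.2 leave weight and renal function out of the simulated efficacy and toxicity probabilities?

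*Combined protocol and SAP*

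**What the plan says.** Aim 4.2 is to "assess the effect of patient-specific covariates (e.g., body weight, renal function) on PK parameters". It adds that earlier studies suggest clearance is unrelated to body weight and "have discordant results regarding patient renal function".

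Section 6.1.1 describes one- and two-compartment models, individual Bayesian estimates and scatter plots for each patient. Section 6.3.2 chooses between models by -2LL, AIC and diagnostic plots. Neither section names covariates.

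Section 6.1.2 takes its prior from the fitted model: "The parameter vector and covariance matrix from population PK modeling will be used as the prior distribution for the simulation function". It continues: "1000-subject Monte Carlo simulations will be performed for candidate dosing regimens". AUC is computed as "values for different 24-hour increments through 96 hours". For each regimen, the "probability of efficacy will be the fraction of the simulated subjects at each time interval" with 24-hour AUC of 50–100 mg*h/L; toxicity is the fraction at or above 100. No covariate value, distribution or stratum appears, and the regimens are not listed.

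The local schedule in Section 5.6.2 uses weight twice. The loading dose is 2 mg/kg with a 200 mg cap, and the step from 100 mg to 75 mg every 12 hours is "recommended for patients with total body weight less than or equal to 50 kg".

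**The concern.** Aim 4.2 asks whether weight and renal function alter the kinetics. Section 7.1.1 says the data will be used to confirm dosing in this population, and the simulated probabilities are the planned output that bears on dosing. Nothing in Section 6 joins the two explicitly. Read literally, one set of parameters feeds one pooled fraction per regimen and interval. A weight or renal effect found in the model would then be averaged away. Patients at or below 50 kg, or with unusually high or low renal function, would be the ones misdescribed.

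There is a related worry. Section 3 doubts the renal effect in the earlier cystic fibrosis study because one patient produced most of it. This plan is also small: the supply count in Appendix I allows for up to 20 subjects. Yet it names no covariate-parameter pairs to test and no formal influence check.

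**Working it through.** **1. The text, in order.** The end of Section 3 and Aim 4.2 make the population model the tool for assessing weight and renal function. Section 5.8 collects weight, height, age, sex and serum creatinine, partly for building that model. Section 6.3.2 supplies criteria that can compare models with and without a covariate. Section 6.1.2 simulates from the resulting model. Two cases follow.

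- *A covariate is retained*, for example CL = typical CL × (weight / reference weight)^b. No curve can be generated until a weight is supplied, so the analyst has to choose covariate values.
- *No covariate is retained.* There is no effect to carry forward. Section 6.1.2 scores each regimen separately, so the 75 mg and 100 mg schedules can be run as two regimens, each with a load matched to its weight group.

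**2. Size of the possible error.** The documents give no PK values and no target-attainment figure to reproduce, so these inputs are assumptions: mean CL 2.5 L/h with CV 40%; V with CV 30%; half-life 12 h; one compartment; 1 h infusion; weight mean 60 kg, SD 12, floored at 30 kg. About 20% then weigh 50 kg or less, with group mean 43.4 kg. Total log-scale variance is held fixed when a weight exponent is added.

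Per-interval AUC = (drug in body at start + dose given − drug in body at end) / CL. The weight-linked run gives each subject the Section 5.6.2 schedule. The weightless run uses the pooled CL and V draws, the same maintenance dose and a load of 2 × 43.4 = 86.8 mg. I reran this with 1,000,000 draws. Results at or below 50 kg, weight-linked v weightless:

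| Weight effect | Day 1, P(50–100) | Day 4, P(50–100) | Day 4, P(≥100) |
|---|---|---|---|
| None | 22% v 21% | 64% v 64% | 10% v 10% |
| V proportional | 46% v 21% | 63% v 64% | 12% v 10% |
| CL proportional | – | 65% v 64% | 29% v 10% |
| Both proportional | 75% v 25% | 61% v 63% | 34% v 11% |
| Exponent 0.5 on both | 43% v 22% | 66% v 64% | 20% v 10% |

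The efficacy gap is a first-day effect; by day 4 it is about 2 points or less. The toxicity gap persists when clearance depends on weight. Levels depend on reading 2.5 L/h as a mean: taken as a median, the no-effect day-1 figure is 16% rather than 22%.

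**3. Renal function, steady state, 200 mg/day.** AUC24 = 200/CL, so AUC ≥ 100 means CL ≤ 2 L/h. With mean 2.5 and CV 40%, σ = √ln(1.16) = 0.385 and μ = ln 2.5 − 0.385²/2 = 0.842. Then P(AUC ≥ 100) = Φ((ln 2 − 0.842)/0.385) = Φ(−0.39) = 35%. With CL proportional to CrCL^0.5 and log CrCL SD 0.25, the bottom CrCL quartile has 51% and the top 20%. With exponent 0, every quartile has 35%.

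**4. What prespecified strata and checks would add.** With 20 patients, 20% of them at or below 50 kg, that group has about 4 members (95% range 1–8). In a regression analogue with n = 20, log CL SD 0.385 and log weight SD 0.198, AIC retains a null covariate about 19% of the time and a true exponent of 0.5 about 43% of the time. For influence, one outlying patient (3 SD high in log CrCL, twice the typical CL) moves the mean slope from 0.00 to 0.31. Leave-one-out refits give a median largest slope shift of 0.30 with that patient and 0.23 without.

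**The case for a change.** The best case for a change is that necessity does not dictate *how* the gap is filled. With a retained covariate, an analyst could fix every simulated subject at a typical weight and creatinine clearance, or draw values from the enrolled cohort, or stratify. These give different probabilities, and the table shows that the differences can be large. The evidence in Section 3 against a weight effect concerns clearance, while an effect on volume alone moves day 1. The local schedule is itself weight-based, so some weight or group-matched load is needed whatever the kinetics. The cost would be a few sentences.

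Most of this stands as fact. Section 6.1.2 is silent on covariate values and regimens, and no other section supplies them. What does not stand is the step from silence to consequence. No sentence says that covariates are excluded or that results are pooled over weight groups; the scoring is by regimen. The large gaps arise only if an effect is found and then ignored by analysts whose stated aim was to look for it.

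The influence point has some force, and the outlying patient is the most influential in 81% of replicates. But shifts of 0.30 and 0.23 separate poorly, and the individual estimates and plots in Section 6.1.1, though not a formal check, already put an odd patient in view.

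**Conclusion.** This is missing detail that analysts must fill to run the simulation, not a rule that gives a wrong answer. If weight has no effect on PK, leaving individual weights out costs about 1 point on day 1 and nothing on day 4. If an effect is retained, the model needs covariate values before it can be simulated, and the data are already collected. The worst illustrative errors at or below 50 kg are 75% v 25% for day-1 efficacy and 34% v 11% for day-4 toxicity. They need clearance and volume both fully proportional to weight and a simulation that disregards it. The clearance part runs against the studies cited in Section 3. All these figures rest on assumed kinetics.

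The study is small and non-interventional, and Section 5.6.1 leaves dosing to the prescriber. Fixing strata and influence checks in advance would bring little when the lighter group may hold about 4 patients. The report can say which covariate values and regimens were simulated. No change to the plan is called for.

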6.3. Statistical Analysis

6.3.1. Baseline demographic and clinical data: Baseline demographic and clinical data will be assessed using descriptive statistics. Variables will be summarized as mean (standard deviation), median (5th, 95th percentile), or number (percentage) as indicated.

6.3.2. Population pharmacokinetic analysis: Model goodness-of-fit of the observed data will be assessed by regression with an observed-predicted plot. Between-subject variability will be quantified using coefficients of determination. Model discrimination will be based on log-likelihood (-2LL) and Akaike's Information Criterion (AIC) objective function values as well as diagnostic plots. Predictive performance evaluation will be based on weighted mean bias and the bias-adjusted weighted mean precision.

6.3.3. Toxicity analysis: Nephrotoxicity and neurotoxicity rates will be summarized as number (percentage). Time to renal recovery will be summarized as mean (standard deviation) or median (interquartile range) days as indicated while renal recovery by hospital discharge will be summarized as number (percentage).

7. Benefits and Risks

7.1. Benefits:

7.1.1. Current CF Foundation guidelines recommend that two antibiotics with activity against *P. aeruginosa* as the standard of care for treatment of acute pulmonary exacerbations. Many adult CF patients have had extensive lifetime exposure to antipseudomonal antibiotic therapy and may require therapy with last line agents due to multi-drug resistance in clinical isolates. The polymyxins, colistin and polymyxin B, are often required as combination salvage therapy for isolates with documented resistance to aminoglycosides or fluoroquinolones. Polymyxin B has significant pharmacokinetic advantages to colistin for CF patients; however, limited data exist in this patient subpopulation to guide dosing in practice. The data generated by this study will be used to confirm dosing of polymyxin B in this population and ensure safety with commonly administered doses extrapolated from non-CF patient populations. There is no direct benefit to patients enrolled in the study at the time of enrollment; however, patients treated with polymyxin B at the time of the study are at risk for re-infection with MDR organisms in the future. Therefore, PK data obtained in this study could inform the dosing of polymyxin B for the treatment of future infections with MDR organisms.

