10.1. Appendix I: Laboratory Protocol

Laboratory Protocol

1. Blood Collection Tubes

Plastic Lavender Top K2-EDTA Tube (BD, Franklin Lakes, NJ, Catalog# 367863)

2. Blood Collection Supply Quantities

Five blood samples are to be obtained and processed per subject on polymyxin B therapy. Samples will be collected at the time points listed below relative to the end of polymyxin B infusion (t_{inf})

Sample Code	Collection Timepoint	Collection Time Relative to Duration of Infusion (t_{inf})
C_0	Prior to Start of Infusion	0 hour
C_1	End of Infusion	$t_{inf} + 0$ hour
C_2	One Hour after End of Infusion	$t_{inf} + 1$ hour
C_3	Three Hours after End of Infusion	$t_{inf} + 3$ hours
C_4	Eight Hours	8 hours

Minimum Supplies Necessary:

Up to 20 subjects \times 5 blood collection tubes = 100 Blood Collection Tubes
 100 blood samples \times 2 plasma aliquots/blood sample= 200 cryovials (Screw Capped Polypropylene, 1-2 mL)
 200 cryovials \times 1box/81 cryovials= 3 cryovial storage boxes

3. Pre-Study Preparation

a. Plasma collection tubes

- i. Label 5 plasma collection tubes per subject with:
 - 1) study protocol number
 - 2) the study subject code
 - a) color code with a highlighter pen (yellow, pink, green, orange) the subject code if more than one subject is to be studied on the same date
 - 3) date of collection

- 4) sample code (i.e. C₀, C₁, etc.)
 - ii. Transfer plasma collection tubes to a test-tube rack
 - 1) Individual test-tube racks should be used for each subject if more than one subject is to be studied on the same day
 - iii. Pre-chill (2-8°C) plasma collection tubes prior to blood collection
 - b. Cryovials
 - i. Label 10 cryovials per subject with:
 - 1) study protocol number
 - 2) the study subject code
 - a) color code with a highlighter pen (yellow, pink, green, orange) the subject code if more than one subject is to be studied on the same date
 - b) the color code should match the plasma collection tube for each subject to reduce the risk of potential transfer error
 - 3) date of collection
 - 4) sample code (i.e. C₀, C₁, etc.)
 - 5) aliquot number (AQ-1, AQ-2)
 - ii. Transfer cryovials to a rack
 - 1) Individual cryovial racks should be used for each subject if more than one subject is to be studied on the same day
 - c. Cryovial boxes
 - i. Label 2 cryovial boxes with:
 - 1) study protocol number
 - 2) date of collection
 - 3) aliquot number (AQ-1 and AQ-2)

4. Blood Sample Collection and Processing

- a. Collection

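### The simulated probabilities of efficacy and toxicity are planned without an interval, although the population model behind them rests on up to 20 patients

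*Combined protocol and SAP*

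**What the plan says.** Section 6.1.2 sets out the simulation: "The parameter vector and covariance matrix from population PK modeling will be used as the prior distribution for the simulation function within Pmetrics™", and then "1000-subject Monte Carlo simulations will be performed for candidate dosing regimens". The two outputs are defined as fractions of those simulated subjects. For efficacy, "probability of efficacy will be the fraction of the simulated subjects at each time interval" with a 24-hour AUC of 50–100 mg*h/L. For toxicity, "the probability of toxicity will be the fraction of subjects with 24-hour AUC values" of at least 100 mg*h/L.

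The data behind the fit are described elsewhere. Section 5.7.1 says "Blood samples will be collected from enrolled patients at 5 time points during a single dosing interval under steady-state conditions". There is no sample-size section. The only patient number is "Up to 20 subjects" in the supply list of the laboratory appendix (10.1).

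Section 6.3.2 covers evaluation of the model: observed-predicted regression, -2LL and AIC, diagnostic plots, and "Predictive performance evaluation will be based on weighted mean bias and the bias-adjusted weighted mean precision". Neither 6.1.2 nor 6.3.2, nor any other section, plans a standard error, a confidence or credible interval, or a bootstrap for the two probabilities. Section 7.1.1 says that the study's data "will be used to confirm dosing of polymyxin B in this population".

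**The concern.** The covariance matrix in 6.1.2 serves as the distribution from which virtual patients are drawn. It therefore describes how patients differ from one another, and nothing in the text says that it also carries uncertainty in the estimated mean and spread. The statistics in 6.3.2 describe fit to the patients who were sampled, not how far the estimated population could lie from the true one.

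A fraction from 1000 simulated subjects, reported alone, therefore shows the reader nothing of the small number of real patients behind it. The protocol is alert to this weakness in other work: Section 3 doubts a covariate result from the earlier nine-patient CF study because one patient drove most of it. If point fractions are later cited in support of a regimen, readers may take them as better established than they are.

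**Working it through.** **Plan's own figures.** There is no stated sample size, power or precision to reproduce. The supply arithmetic is correct: 20 × 5 = 100 tubes; 100 × 2 = 200 cryovials; 200/81 = 2.5, so 3 boxes.

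**Inputs.** From the documents: up to 20 patients (10.1); 1000 simulated subjects and the AUC bands (6.1.2); 100 mg every 12 hours, which is 200 mg/day (5.6.2). Assumed, because the documents give no values: lognormal clearance (CL), median 2.0–3.0 L/h, CV 25–45%, first-order elimination at steady state so that AUC24 = dose/CL, and each patient's CL known without error.

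**Monte Carlo error.** Half-width = 1.96 × sqrt(p(1−p)/1000). The maximum is at p = 0.5: 1.96 × sqrt(0.25/1000) = 3.1 points.

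**True fractions, central case (median 2.5, CV 35%).** With AUC24 = 200/CL, efficacy means CL between 2 and 4 L/h, and toxicity means CL of 2 L/h or less. The log-scale SD is sqrt(ln(1 + 0.35²)) = 0.340.
- Toxicity: Φ(ln(2/2.5)/0.340) = Φ(−0.656) = 25.6%.
- Efficacy: Φ(ln(4/2.5)/0.340) − 25.6% = 91.7% − 25.6% = 66.1%.

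**Sampling error from 20 patients.** 20,000 studies were simulated. In each, the mean and SD of log CL were estimated from 20 patients and both fractions recomputed. The table gives the true value, the central 95% range of the estimates, and half the width of that range.

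| Median CL, CV | Efficacy, % | Half-width | Toxicity, % | Half-width |
|---|---|---|---|---|
| 2.0, 25% | 49.8 (32.0–67.3) | 17.6 | 50.0 (32.0–67.9) | 17.9 |
| 2.5, 25% | 78.9 (64.6–92.6) | 14.0 | 18.2 (5.6–32.5) | 13.4 |
| 2.5, 35% | 66.1 (51.9–82.0) | 15.0 | 25.6 (10.6–41.2) | 15.3 |
| 2.5, 45% | 56.1 (43.3–72.5) | 14.6 | 30.2 (13.7–46.6) | 16.5 |
| 3.0, 25% | 82.9 (69.1–94.7) | 12.8 | 5.0 (0.5–13.7) | 6.6 |
| 3.0, 45% | 57.6 (44.5–74.2) | 14.8 | 17.3 (5.0–31.4) | 13.2 |

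Over the whole 3 × 3 grid the efficacy half-width runs from 12.8 to 17.6 points. With 10 patients the central efficacy range widens to 46–89%. Setting the calculation up directly on AUC (median 60–90 mg*h/L, CV 30–50%, 20 patients) gives half-widths of 14.0–16.3 points for efficacy and 5.8–17.7 for toxicity.

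**Differences between regimens.** Both regimens are evaluated from the same fitted distribution, so the error was computed on the paired difference in efficacy. The two maintenance totals in 5.6.2 (200 and 150 mg/day) serve purely as arithmetic examples, with 20 patients:
- Median 2.5, CV 35%: true difference about 2 points in favour of 200; estimates from −15 to +21; wrong sign in 39% of studies.
- Median 2.3, CV 25%: true difference 11.6 points in favour of 150; estimates from about −8.5 to 31; wrong sign in about 13%.
- Median 3.0, CV 45%: true difference 12.9 points in favour of 200; estimates from 1.0 to 29.7; wrong sign in about 2%.

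**The case against.** The strongest reply is that this is a descriptive, single-centre PK study. Its aims (4.1–4.3) are to measure concentrations, characterise PK and covariates, and describe safety. No section ranks or selects a regimen, and the plan claims no precision for the fractions. Section 7.1.1 says that the study's data will confirm dosing, not that these two fractions will. All of that stands. It limits what is at stake, but it does not supply the missing interval.

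Three stronger readings are tempting, and none is supported:
- A reader might infer that about 15 points applies to both fractions throughout. For toxicity it does not: the error shrinks as the true probability falls, to about 6.6 points at a true 5%.
- A reader might infer that any 10-point difference between regimens is lost in sampling error. That takes the error of one fraction for the error of a difference. Two true differences of similar size above behave differently: at 11.6 points the range includes zero, and at 12.9 points it does not.
- A reader might infer that too few simulated subjects is the problem. More of them would reduce only the 3.1 points and leave the uncertainty from the patients untouched.

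It can also be said that the magnitudes rest on clearance values that the documents do not contain. That is correct. The omission is certain; its size is conditional on the assumptions.

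**Conclusion.** The concern holds as a gap in reporting. Section 6.1.2 treats a distribution estimated from up to 20 patients as known, and nothing in the plan carries that estimation uncertainty into the two probabilities.

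Under the stated assumptions, the uncertainty of the efficacy fraction is roughly four to six times the maximum Monte Carlo error (12.8/3.1 = 4.1; 17.6/3.1 = 5.7). For toxicity it is comparable when the true probability is about 20% or more, and smaller below that. The calculation leaves out error in each patient's clearance, the choice among structural models, and covariate selection, all of which would normally widen the ranges. The count of 20 is a supply maximum, and fewer patients would widen them further. The steady-state formula fits the later 24-hour increments best; early ones also depend on the loading dose and volume of distribution.

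No general statement about regimen comparisons follows. The change is worth making because it is cheap and keeps point fractions from overstating how well a regimen is supported.

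**What to change.** Add to 6.1.2: patients will be resampled with replacement (for example, 200 bootstrap samples); the final model will be refitted to each sample and the simulation repeated; each efficacy and toxicity fraction will be reported with its 2.5th–97.5th percentile interval. Any between-regimen difference that is reported should be computed within each bootstrap sample, so that shared error cancels, and given with the same kind of interval. A matching sentence in 6.3.2 would keep the two sections consistent.

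Optionally, show beside these the observed fraction of enrolled patients whose own Bayesian AUC24 falls in each band, with an exact binomial interval.

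The cost is two or three sentences and the computer time for repeated refits. No patients, samples or changes in care are needed. The intervals will be visibly wide. With 20 or fewer patients the bootstrap is itself approximate, and refitting only the final model leaves model-selection uncertainty out; the report should say so.

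### Does calling attainment of a 24-hour AUC of 50 to 100 mg*h/L the probability of efficacy hide underexposure in the simulations?

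*Combined protocol and SAP*

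**What the plan says.** Section 6.1.2 (Monte Carlo Simulation) states that "1000-subject Monte Carlo simulations will be performed for candidate dosing regimens". For each regimen, the 24-hour AUC is computed in successive 24-hour periods up to 96 hours, and two summaries follow in a single sentence:

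- Efficacy: "probability of efficacy will be the fraction of the simulated subjects at each time interval for which the 24-hour AUC is between 50" to 100 mg*h/L.
- Toxicity: "the probability of toxicity will be the fraction of subjects with 24-hour AUC values ≥ 100 mg*h/L".

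Neither 6.1.2 nor 6.3.2 names the fraction below 50 as an output. No rule in the document picks a regimen from the efficacy figure.

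Two other places give context. Aim 4.2 says of earlier work that "These studies suggest that the clearance of PMB is not related to patient body weight", and concludes that underweight patients with good renal function "may be at risk for underdosing with traditional weight-based regimens". Section 5.6.2 describes the local recommendation: after a loading dose, maintenance "followed by 100 mg every 12 hours for the duration of therapy", and for patients of 50 kg or less "A reduction of the maintenance dose to 75 mg every 12 hours is recommended".

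**The concern.** The word efficacy suggests a one-sided quantity: the chance of enough exposure. What is defined is a window. A simulated subject at or above 100 counts as toxic and also as not efficacious, although 6.1.2 does not argue that the drug stops working there. The figure equals P(AUC24 ≥ 50) minus P(AUC24 ≥ 100), cannot exceed 1 − P(AUC24 ≥ 100), and must eventually fall as exposure rises.

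Two consequences look troubling. First, the figure alone does not tell underexposure from overexposure. Second, a lower-exposure regimen can show higher efficacy while more of its subjects lie below the plan's own lower bound. Aim 4.2 is worried about underdosing, and 7.1.1 says the results will serve to confirm dosing. If a reader compared regimens on the efficacy figure alone, the band of most interest would go unseen.

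**Working it through.** **Inputs from the document.** Limits of 50 and 100 mg*h/L and 1000 simulated subjects (6.1.2); maintenance totals of 2 × 100 = 200 and 2 × 75 = 150 mg/day (5.6.2), used here only as two exposure levels. The document states no attainment figure to reproduce and no clearance (CL) distribution, so every CL value below is an assumption.

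**Step 1: what the two outputs determine.** Every simulated AUC24 falls below 50, in 50 to 100, or at or above 100. Hence

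- P(<50) = 1 − efficacy − toxicity
- P(≥50) = efficacy + toxicity

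This needs no distribution and no elimination model. It holds for the first-order base model ("elimination from the central compartment modeled as a first-order process") and for the Michaelis-Menten alternatives in 6.1.1. An AUC of exactly 100 would fall in both bands if the window includes its upper end, but for a continuous AUC this has probability zero.

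**Step 2: is the direction of a miss lost?** Take a lognormal AUC24 with assumed CV 40% and two medians placed symmetrically about √(50 × 100) = 70.7: 70.7/1.5 = 47.1 and 70.7 × 1.5 = 106.1.

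| Median AUC24 | Efficacy | Toxicity | 1 − efficacy − toxicity |
|---|---|---|---|
| 47.1 | 0.414 | 0.025 | 0.561 |
| 106.1 | 0.414 | 0.561 | 0.025 |

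Efficacy alone cannot tell these apart. The pair that the plan reports does so at once.

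**Step 3: the apparent reversal.** At steady state with first-order elimination, AUC24 = D/CL. The window is then D/100 < CL ≤ D/50: 2 to 4 L/h for 200 mg/day and 1.5 to 3 L/h for 150 mg/day. With F the distribution of CL, efficacy = F(D/50) − F(D/100) and toxicity = F(D/100). For lognormal CL, CV 40%:

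| Assumed median CL | mg/day | Efficacy | Toxicity | Below 50 | Outside window |
|---|---|---|---|---|---|
| 2.0 L/h | 200 | 0.464 | 0.500 | 0.036 | 0.536 |
| 2.0 L/h | 150 | 0.626 | 0.228 | 0.146 | 0.374 |
| 3.0 L/h | 200 | 0.626 | 0.146 | 0.228 | 0.374 |
| 3.0 L/h | 150 | 0.464 | 0.036 | 0.500 | 0.536 |

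At a median of 2.0 the lower level scores higher on the window. The fraction below 50 rises by 0.146 − 0.036 = 0.110, but the fraction at or above 100 falls by 0.500 − 0.228 = 0.272. The net gain is 0.272 − 0.110 = 0.162 = 0.626 − 0.464. Fewer subjects are outside the limits, which is what the measure is meant to register. At a median of 3.0 the order is the other way round. For lognormal CL the switch is at √6 = 2.45 L/h.

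**Step 4: simulation noise.** With 1000 subjects the standard error at 0.464 is √(0.464 × 0.536/1000) = 0.016. Under an assumed bimodal CL the two efficacy figures are 0.486 and 0.497. That gap of 0.011 is smaller than the standard error of either figure.

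**The case for a change.** The best case for the concern is that labels guide readers. A quantity called efficacy that already has toxicity subtracted invites misreading, and the one band left unnamed is the one Aim 4.2 cares about. At an assumed median CL of 2.0 L/h, the level with the higher efficacy figure has about four times as many subjects below 50 (0.146/0.036 ≈ 4). The direction holds at CV 30% (efficacy 49% at 200 against 75% at 150 mg/day; below 50, 1% against 8%) and at CV 50% (43% against 53%; 7% against 20%). Naming the quantity after the window and tabulating the lower band would cost almost nothing.

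The description of the definition stands: it is a window, the label is loose, and the lower band is not named. The harm does not follow. It needs a reader who sees efficacy without toxicity, and the plan always gives both, with the numeric limits beside the label. It also needs a decision taken on efficacy alone, and there is none. The illustration assumes a clearance the documents do not supply and works at steady state, whereas 6.1.2 looks at every 24-hour period from the start of treatment and 5.6.2 includes a loading dose. Section 6.1.2 does not name 200 and 150 mg/day as its candidates, and 5.6.2 assigns them to different weight groups. Aim 4.2 ties underdosing to weight-based regimens and does not mention the simulations.

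**Conclusion.** The concern does not hold. A two-sided exposure window is a legitimate summary, and paired with the toxicity fraction it describes all three exposure bands completely. Underexposure is one subtraction away for every regimen and interval: 1 − 0.464 − 0.500 = 0.036 in the worked example. That identity rests on no assumption. The reversal between exposure levels is the trade-off a window is meant to express, and its occurrence, size and direction depend on an assumed CL distribution (present at a median of 2.0 L/h, absent at 3.0 L/h). No estimate, threshold, sample size, error rate or stated decision is affected. What remains is a preference about naming. This check does not address whether 50 and 100 are the right limits, and no conclusion about dosing follows from it.
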